2 STUDY OBJECTIVES

2.1 Primary Objective

To evaluate the effect of moderate hepatic impairment on the pharmacokinetics (PK) and pharmacodynamics (PD) of a single oral dose of bexagliflozin tablets, 20 mg

2.2 Secondary Objective

To assess the safety and tolerability of bexagliflozin in subjects with moderate hepatic impairment.

3 INVESTIGATIONAL PLAN

3.1 Overall Study Design and Plan

Approximately 16 subjects (eight with moderate hepatic impairment [Child-Pugh total score 7-9] and eight healthy, matched controls) will be enrolled.

The Child-Pugh grading system will be used to assess the severity and prognosis of hepatic disease. Male or female subjects with hepatic impairment conforming to the Child-Pugh classification of B (Child-Pugh total score 7-9) based on the Child-Pugh scoring method described in [Appendix 2](#) will be enrolled. For each enrolled subject with liver dysfunction a matching control subject (healthy subject) with similar age (± 10 years), weight ($\pm 10\%$), sex, and smoking status will be enrolled.

Each subject will take a single bexagliflozin tablet, 20 mg, with 240 mL of water in the morning (approximately 8 a.m. to 10 a.m.) after an overnight fast. Food will be withheld for at least 2 h postdose. Water will be allowed as desired except for one hour before and after drug administration.

Blood samples for determining the plasma concentrations of bexagliflozin will be collected at predose and at 0.5, 1, 2, 3, 4, 5, 6, 8, 10, 12, 16, 24, 36, and 48 h postdose.

Urine samples for PD analysis will be collected predose and in the following intervals after dosing: 0–12, 12–24, 24–36, and 36–48 h.

Plasma concentrations of bexagliflozin will be determined by validated liquid chromatography-mass spectrometry (LC-MS/MS) methods.

The unbound fraction of bexagliflozin will be determined at 24 h postdose (or earlier if the 24 h postdose sample has a concentration below the limit of quantitation) and at the maximum plasma concentration for each subject by equilibrium dialysis.

Clinical laboratory tests and safety monitoring will be conducted during the treatment period and at the follow-up visit. The study event table is provided in [Appendix 1](#).

3.2 Rationale for Study Design and Control Group

3.2.1 Rationale for Study Design

Pharmacokinetic studies are used to identify special subgroups of patients for whom an alternative dosing regimen may be indicated for efficacy and/or safety reasons. Liver dysfunction of all types, from transient injury to acute liver failure, are common in adult populations. Through a variety of oxidative and conjugative metabolic pathways, the liver is involved in the clearance of many drugs. In addition, the liver directly excretes xenobiotic compounds and their metabolites into bile. Because the liver produces the majority of protein in plasma, hepatic failure can also affect plasma protein binding, which can influence the distribution or elimination of protein-bound drugs.

In this study, the PK, PD and safety profile produced by a single oral dose of bexagliflozin tablets, 20 mg, will be compared between patients with moderate hepatic impairment and demographically matched subjects with normal hepatic function.

3.2.2 Rationale for Dose Selection

Bexagliflozin produces a dose-dependent and saturable UGE in healthy volunteers and diabetic subjects. A population PD model has predicted that bexagliflozin tablets, 20 mg, produced 85% and 94% of the maximal UGE in healthy and diabetic subjects, respectively. Bexagliflozin has consistently demonstrated wide safety margins in clinical and nonclinical studies. .

A single-dose study is considered sufficient since previous studies show bexagliflozin exhibit linear and time-independent pharmacokinetics (THR100-CLR-002).

3.2.3 Rationale for PK and PD Sampling Time Points

Plasma and urine samples will be collected for 48 hours after dosing. The excretion of total radioactivity in urine occurred principally in the first 48 h following oral dose of [¹⁴C] - bexagliflozin in humans (THR-1442-C-410).

3.3 Study Duration and Dates

This is a single dose study. Selection and enrollment of study subjects will begin with those designated for the hepatic impairment group. A screening visit will be completed 2 to 28 days prior to study drug administration. Subjects will be admitted to the clinic the day before administration of the investigational product and will remain in the clinic for at least 48 h following administration. Subjects will return for an end-of-study examination within 13 days of the last pharmacokinetic sample collection. Each subject from the hepatic impairment group will be matched to a healthy comparator subject. For details of the schedule and nature of the investigations, see the Schedule of Events in [Appendix 1](#).

4 STUDY POPULATION SELECTION

4.1 Study Population

The study population comprise eight subjects with hepatic impairment conforming to the Child-Pugh class B (Child-Pugh total score 7-9) and eight control subjects (healthy subjects with normal hepatic function). Each healthy control subject will be matched with an individual subject in the hepatic impairment group by age (± 10 years), weight ($\pm 10\%$), sex, and smoking status.

Eligible subjects who consent to participate in the study will be enrolled in clinical investigational sites in the United States. Study subjects will be informed of the purpose and potential risks of participation in the study.

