1 INTRODUCTION

Bexagliflozin is a potent and selective inhibitor of human sodium-glucose linked transporter 2 (SGLT2). The clinical pharmacology of bexagliflozin is largely consistent with the expected consequences of SGLT2 inhibition. The primary pharmacodynamic effect is a glucosuria that increases with glomerular filtration rate and plasma glucose concentration. Effects secondary to diuresis, possible natriuresis, and caloric wasting, including reductions in blood pressure and body weight, have been observed. Consistent with clinical observations that individuals genetically deficient for SGLT2 are euglycemic and normotensive to slightly hypotensive, inhibition of SGLT2 function does not appear to confer a risk of hypoglycemia or of significant hypotension. Mild hemoconcentration associated with volume depletion attributed to the diuretic effect has been observed. Slight elevations in blood urea nitrogen (BUN) and creatinine, and corresponding inferred decreases in estimated glomerular filtration rate (eGFR), have typically accompanied the pharmacodynamic response and are considered to be consistent with diuresis and metabolic shifts favoring protein catabolism. Moderate reductions in plasma urate and small increases in LDL cholesterol concentration that appear to be class effects have yet to be explained.

Bexagliflozin tablets, 20 mg, are blue caplet-shaped film-coated tablets with a gastroretentive mechanism based on mucoadhesion. Peak plasma bexagliflozin concentrations are observed 3 to 5 h after dosing and thereafter decline in a biphasic manner with mean elimination half-life values ranging from 7.8 to 9.7 h. Bexagliflozin is extensively metabolized, predominantly to a 3'-*O*-glucuronide, but also to a mixture of additional glucuronides and oxidation products. .

The relative contributions of different organs to metabolism of bexagliflozin are not known. Cytochrome P450 oxidases are found in intestine, kidney and liver, with the latter usually considered the most important site for xenobiotic oxidation. Glucuronidation is principally carried out in the kidney and liver. Because high amounts of [¹⁴C]-bexagliflozin have been observed in the kidney in rats and renal recirculation of the compounds appears likely, a significant renal contribution cannot be excluded.

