Dose-titration studies have shown that the primary pharmacodynamic effect, urinary glucose excretion (UGE), can be described in both healthy and diabetic subjects by a simple logistic equation. The median effective dose (ED₅₀) is estimated to be 3.6 mg in healthy subjects and 1.2 mg in diabetic subjects. From this, a 20 mg dose is expected to produce 85% or 94% of the theoretical maximum UGE in healthy or diabetic subjects, respectively. After a single dose of bexagliflozin, diabetic subjects have exhibited significant glucosuria and experienced meaningful reductions in fasting plasma glucose (FPG). Healthy and diabetic subjects have also experienced a moderate diuretic effect. The dose-related glucosurias observed in Japanese and American populations have been similar in magnitude.

Although bexagliflozin is a potent glucosuric agent, hypoglycemia and hypotension have not been observed in the setting of monotherapy. All reports of hypoglycemia and hypotension have occurred in the context of additional anti-diabetic or anti-hypertensive agents. Insulin and insulin secretagogues of the sulfonylurea class have been frequently implicated in bexagliflozin-associated hypoglycemia.

SAFETY INFORMATION FROM HUMAN EXPOSURE

Bexagliflozin has been well tolerated whether administered as immediate release capsules or extended release tablets. The proportion of subjects who have experienced any treatment-emergent adverse event (AE) has been comparable between active and placebo arms. The most frequently occurring AEs (> 5%) have been urinary tract infections and hypoglycemia. For both types of event, the rate has been higher in the combined placebo group than in the combined bexagliflozin groups (of all strengths). Similarly, taking all completed studies into consideration, a higher percentage of subjects in the placebo or comparator groups have experienced serious adverse events (SAEs) than subjects in the bexagliflozin treatment groups, taking all dosage levels combined. Neither death nor serious adverse event has been observed in any of the phase 1 clinical pharmacology studies. Deaths have occurred in multiple phase 2 and 3 studies, particularly in a large, ongoing cardiovascular safety study.

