4.2 Inclusion Criteria

Prospective subjects must:

1. Be male or female adults between the age of 18 to 75 years (inclusive) at screening
2. Have a body-mass index (BMI) of 18.0 - 40.0 kg m⁻² (inclusive) at screening
3. Have adequate venous access at multiple sites in both arms
4. Be willing and able to be confined to the clinical research facility as required by the protocol
5. Be able to comprehend the explanation of the informed consent and be willing to provide written informed consent in accordance with institutional and regulatory guidelines
6. Be diagnosed with moderate hepatic impairment with a Child-Pugh score 7 to 9 (classification in [Appendix 2](#)) and must be in stable general health apart from hepatic impairment and its related conditions (**for subjects in the hepatic impairment group only**)
7. Be in general good health with matching demographics and baseline characteristics to individual subjects in the hepatic impairment group by age (± 10 years), weight ($\pm 10\%$), sex, and smoking status (**for subjects in the healthy control group only**)
8. Have no evidence of an active infection or be receiving any treatment with antibiotics at the time of screening (**for subjects in the healthy control group only**)

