24. If destined for the hepatic impairment group, a history of fluctuating or rapidly deteriorating hepatic function or the production of widely varying or worsening clinical and/or laboratory signs of hepatic impairment within the screening period
25. If destined for the healthy control group, a history of prescription or over-the-counter (OTC) drug use within 7 days or 5 half-lives of the drug, whichever is longer, prior to D0
26. If destined for the healthy control group, a history of liver disease or liver injury as indicated by an alanine aminotransferase (ALT), aspartate aminotransferase (AST), > 2.5 × the upper limit of normal (ULN) at screening, or serum bilirubin > 1.5 × ULN
27. If destined for the healthy control group, evidence of HBV or HCV infection.
28. Any other serious medical condition that, in the opinion of the investigator, would pose a significant risk to the subject or interfere with the interpretation of safety, PK, or PD data.

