7.3 Pharmacodynamic Analyses

Urinary glucose excretion (UGE) and creatinine normalized UGE (nUGE) will be determined as PD parameters at baseline and up to 48 hours post-dose.

UGE_{t1-t2} (g) will be derived from urine volume and glucose concentration as follows:

[urine volume (V_{t1-t2} , mL) x glucose concentration (mg/dL)/100]/1000.

UGE normalized by urinary creatinine will be calculated as per below:

[urine volume (V_{t1-t2} , mL) x creatinine concentration (mg/dL)/100]/1000.

The total 24-hour and 48-hour quantity of glucose excreted in urine will be calculated by adding the amounts collected during each post-dose interval.

Descriptive statistics will be used to describe any differences in these PD parameters between treatment groups (normal hepatic function and moderate hepatic impairment).

For PD data, reported pre-dose values that are below the defined limit will be set to zero. Any missing values or values below the reported defined limit that appear after pre-dose for PD data (glucose, UGE, creatinine) will be set to missing. Because zero values cannot be included in calculation of a geometric mean, then geometric means and percent CV calculated for data including values below the defined limit will be based only on the subjects without such zero value data

PD data will also be reported in listings.

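### The urinary glucose comparison in the primary PD objective is open to confounding by glycaemia, and to a lesser degree by eGFR, and SAP 7.3 has no sensitivity summary to show it

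*Protocol*

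**What the plan says.** PD stands beside PK in the primary objective (Protocol 2.1; SAP 2.1). Protocol 9.2 considers the sample of about 8 + 8 adequate for clinically relevant PK or PD differences, so the UGE contrast is meant to be interpreted.

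**Drivers of UGE.** Protocol 1: "The primary pharmacodynamic effect is a glucosuria that increases with glomerular filtration rate and plasma glucose concentration". Protocol 1.2: "The median effective dose (ED₅₀) is estimated to be 3.6 mg in healthy subjects and 1.2 mg in diabetic subjects".

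**Matching.** Protocol 4.1: "Each healthy control subject will be matched with an individual subject in the hepatic impairment group by age" (±10 years), plus weight (±10%), sex and smoking status.

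**Hepatic group.** Under Protocol 4.2 these subjects "must be in stable general health apart from hepatic impairment and its related conditions". Exclusion 23 bars only prescriptions that are new within 30 days, and Protocol 5.6 asks for an unchanged dose and frequency. SGLT2 inhibitors are the only glucose-lowering class that the criteria name as barred (exclusion 5).

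**Control group.** Protocol 4.2: "Be in general good health with matching demographics and baseline characteristics to individual subjects in the hepatic impairment group". Exclusion 25 removes anyone with: "If destined for the healthy control group, a history of prescription or over-the-counter (OTC) drug use within 7 days or 5 half-lives" (whichever is longer).

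**Both groups.** eGFR below 60 mL/min per 1.73 m² is excluded (exclusion 12). No criterion mentions diabetes, glucose or HbA1c.

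**Analysis.** SAP 7.3: "Descriptive statistics will be used to describe any differences in these PD parameters between treatment groups". Protocol 9.6 is likewise descriptive. Neither section adjusts, stratifies or plans a sensitivity analysis for glycaemia or eGFR.

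**The concern.** The protocol names two determinants of the PD endpoint, then neither matches on them nor adjusts for them. For one of them the entry rules are asymmetric: a diabetic subject on stable medication can enter the hepatic group, while the drug-free rule keeps the same subject out of the control group.

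If several diabetic subjects enter the hepatic group, its UGE could be higher for a reason other than liver function. That could create an apparent increase or hide a true reduction. A lower eGFR in the hepatic group would push the other way. With eight subjects per group, a few individuals can move a group summary noticeably, and the planned tables would not show whether a difference, or the absence of one, came from glycaemia.

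**Working it through.** **1. The plan's own PD figure.** Protocol 1.2 describes UGE by a simple logistic equation and predicts 85% (healthy) and 94% (diabetic) of maximum UGE at 20 mg. With fraction = dose/(dose + ED50):

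- healthy: 20/(20 + 3.6) = 84.7%
- diabetic: 20/(20 + 1.2) = 94.3%

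Both figures reproduce. Their ratio is 0.943/0.847 = 1.11, but it compares fractions of each population's own maximum. It leaves out any difference in filtered glucose, and the documents give no absolute UGE. It therefore does not measure the total UGE difference.

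**2. Filtered glucose load.** Load (g/day) = GFR (mL/min) × glucose (mg/dL)/100 × 1440/1000. At an assumed GFR of 90:

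- glucose 90 mg/dL: 90 × 0.90 × 1.44 = 116.6 g/day
- glucose 180 mg/dL: 90 × 1.80 × 1.44 = 233.3 g/day

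This shows where a twofold ratio could come from. The glucose values are assumed, and the protocol says only that glucosuria increases with glucose, not that it is proportional to it.

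**3. Possible shift from glycaemia.** Let k of 8 hepatic subjects be diabetic, with no diabetic controls and no hepatic effect, and let R be the diabetic/non-diabetic UGE ratio. The ratio of geometric means is then R^(k/8). Neither k nor R is in the documents, so both are varied.

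| k | R = 1.25 | R = 2 |
|---|---|---|
| 0 | 1.00 | 1.00 |
| 1 | 1.03 | 1.09 |
| 2 | 1.06 | 1.19 |
| 3 | 1.09 | 1.30 |
| 4 | 1.12 | 1.41 |

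For arithmetic means the ratio is (8 − k + kR)/8. At k = 2 it is (6 + 2.5)/8 = 1.06 for R = 1.25 and (6 + 4)/8 = 1.25 for R = 2. At k = 4 it is (4 + 5)/8 = 1.13 and (4 + 8)/8 = 1.50.

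**4. Possible shift from eGFR.** If UGE were proportional to GFR, assumed group means of 75 and 90 would give a ratio of 75/90 = 0.83. The common floor of 60 allows this. Nothing in the documents says that it will occur.

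**5. Does anything already planned remove the glycaemia difference?** Creatinine normalisation does not, because dividing by creatinine takes no account of plasma glucose. In addition, the expression printed for normalised UGE in SAP 7.3 multiplies urine volume by creatinine concentration and has no glucose term, so as written it cannot adjust UGE. The −12 to 0 h urine gives a baseline value, but the plan does not use it to adjust the comparison.

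**The case against.** The strongest reply is that the design permits an imbalance but does not create one. With no diabetic subjects enrolled, the glycaemia shift is nil. Diabetic subjects on stable treatment may have glucose well below 180 mg/dL, which is why the table includes R = 1.25. Exclusion 28 lets the investigator remove subjects with a serious condition that would interfere with interpreting PD data. Medical history is summarised by hepatic function group (SAP 8.3), and laboratory values are both baseline characteristics (SAP 6.1) and summarised (SAP 8.4.2), so an imbalance would be visible. The PD comparison is descriptive, with no hypothesis test (SAP 3.3). The 90% intervals and the 80-125% boundaries apply only to PK parameters (SAP 7.2).

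Much of this stands, and it limits the point. A reader might infer that the comparison is confounded, or that no UGE difference could be attributed to the liver. The documents do not support that, since they give no diabetes count, glucose values or eGFR distribution. Nor do they expressly bar diabetes from the control group: the bar is indirect, and an untreated diabetic control is not named as excluded. They also do not say that eGFR is lower in hepatic subjects, and both groups share the same floor.

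The reply does not close the gap. Exclusion 28 is discretionary, is limited to serious conditions and does not name diabetes. Seeing an imbalance in a baseline table does not show what it did to UGE. A descriptive comparison that serves a primary objective will still be read as an effect of hepatic impairment.

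**Conclusion.** The point holds as a potential confounder of a descriptive comparison. Glycaemia is the main issue because eligibility is asymmetric on it. eGFR is secondary because it is unmatched but has a common floor.

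Under the stated assumptions, the shift in the ratio of geometric means runs from none (k = 0), through 1.03-1.09 (k = 1), to 1.12-1.41 (k = 4). This is an illustration, not a forecast: k and R are assumed, and the plan computes no UGE ratio.

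The point concerns PD only and does not by itself undermine the PK comparison. It also does not show that the eligibility or matching rules must change. Restricting or matching on diabetes or eGFR is a recruitment trade-off, and the analysis can address the issue at little cost.

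**What to change.** In SAP 7.3, pre-specify two additions beside the raw UGE summaries:

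1. UGE0-24 and UGE0-48 by hepatic function group, excluding subjects whose medical history lists diabetes.
2. A supportive summary by group of UGE divided by estimated filtered glucose load over the same interval, taking load as eGFR × Day 1 predose fasting plasma glucose.

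State that the PD conclusion takes both into account alongside raw UGE. The first removes known diabetes. The second also reflects glucose differences in subjects with no recorded diagnosis, and differences in eGFR.

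The cost is SAP wording and one extra table. Medical history (Protocol 6.2) and predose chemistry with glucose and creatinine (Protocol 6.6.1 and 7.3) are already collected. There are three downsides. The first summary has fewer than eight hepatic subjects if any are diabetic. One fasting glucose only approximates the 24 h load, and the 48 h load still less. MDRD eGFR is indexed to 1.73 m², so it should be converted to absolute GFR using the recorded height and weight, or the limitation stated. With groups this small, both summaries are supportive and do not replace raw UGE.

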4.2 Inclusion Criteria

Prospective subjects must:

1. Be male or female adults between the age of 18 to 75 years (inclusive) at screening
2. Have a body-mass index (BMI) of 18.0 - 40.0 kg m⁻² (inclusive) at screening
3. Have adequate venous access at multiple sites in both arms
4. Be willing and able to be confined to the clinical research facility as required by the protocol
5. Be able to comprehend the explanation of the informed consent and be willing to provide written informed consent in accordance with institutional and regulatory guidelines
6. Be diagnosed with moderate hepatic impairment with a Child-Pugh score 7 to 9 (classification in [Appendix 2](#)) and must be in stable general health apart from hepatic impairment and its related conditions (**for subjects in the hepatic impairment group only**)
7. Be in general good health with matching demographics and baseline characteristics to individual subjects in the hepatic impairment group by age (± 10 years), weight ($\pm 10\%$), sex, and smoking status (**for subjects in the healthy control group only**)
8. Have no evidence of an active infection or be receiving any treatment with antibiotics at the time of screening (**for subjects in the healthy control group only**)

4.3 Exclusion Criteria

Subjects who have any of the following attributes will be excluded from the study:

1. A clinically significant history of allergy to drugs or latex (at the investigator's discretion)
2. A positive alcohol or drug result based on urine sample or breathalyzer testing at screening or at clinic admission (D0). A subject may be eligible upon medical monitor

review and approval if the positive urine drug test is from stable dose of prescription medication

3. A record of donation of 400 mL of whole blood within two months, 200 mL of whole blood within one month, or blood components or plasma within 14 days prior to D0.
4. A history of exposure to an investigational drug within 30 days or 5 half-lives of the investigational drug prior to D0, whichever is longer
5. A history of exposure to any SGLT2 inhibitor within 3 months prior to D0 or participation in previous bexagliflozin clinical trials
6. A history of exposure to probenecid, rifampin or any potential strong UGT1A9 inducers or inhibitors within 2 months of D0
7. A clinically significantly abnormal screening ECG that includes but is not limited to: heart rate <40 or >110 bpm, QRS > 160 ms, QTc > 480 ms (corrected by Bazett's formula), or any clinically significant arrhythmia including Mobitz type II 2nd Degree Heartblock, and bifascicular block.
8. If destined for the hepatic impairment group, a seated systolic blood pressure <80 or > 160 , confirmed by repeat or diastolic blood pressure of < 40 or >100
9. If destined for the healthy control group, a seated systolic blood pressure <90 or > 140 , confirmed by repeat or diastolic blood pressure of < 40 or > 90
10. A history of HIV infection or a positive titer for human immunodeficiency virus (HIV) antibody
11. A history of vaccination (with the exception of the flu vaccine) within 30 days prior to D0
12. An estimated glomerular filtration rate (eGFR) < 60 mL min⁻¹ per 1.73 m² as calculated by the modification of diet in renal disease study equation (MDRD), at screening
13. Severe or moderate renal dysfunction or a history of kidney, other organ, bone marrow or stem cell transplant
14. If male, refusing to refrain from donating sperm or use of appropriate birth control when engaging in sexual intercourse for the duration of the study and a period of 14 days after discharge from the clinic. Appropriate birth control methods include condoms with spermicide, female partner's use of diaphragm with spermicide, female partner's use of stable oral, implanted, or injected contraceptive hormones or an intrauterine device. Male subjects who are surgically sterile are eligible
15. If female and of childbearing potential, refusing to use an adequate method of contraception to avoid prevent pregnancy for the duration of the study and a period of 14 days after discharge from the clinic. Adequate methods of contraception for female subjects of childbearing potential include bilateral tubal ligation, intrauterine device, diaphragm with spermicide and male partner's use of male condom with spermicide. Female subjects who are surgically sterile (i.e. have undergone full hysterectomy, or bilateral oophorectomy) or postmenopausal (absence of menses greater than 12 months and age > 45 years) are eligible. All females must have negative pregnancy test at screen and at admission
16. Unwilling to forgo consumption of grapefruit and grapefruit products from 7 days prior to D0 through discharge from the clinic

17. Pre-existing thrombocytopenia (platelet blood count < 30,000 platelets) at screening or other clinically significant findings in CBC
18. A history of current febrile illness, hepatocellular carcinoma, acute liver disease, severe hepatic encephalopathy, or biliary liver cirrhosis
19. A history of significant acute medical illness (new conditions, exacerbation of preexisting conditions or major surgery within 4 weeks of study drug administration), active alcoholic hepatitis, current or recent (within 2 months before D0) history of significant gastrointestinal disease
20. Clinical evidence of severe ascites, as judged by the investigator
21. A history of surgical portosystemic shunt
22. If destined for the healthy control group, a history of vitamin preparation or supplement use (including St. John's Wort and ginseng) within 7 days prior to D0, or caffeine and xanthine containing foods/beverages within 48 h prior to D0
23. If destined for the hepatic impairment group, a history of any new prescription medication within 30 days prior to D0
24. If destined for the hepatic impairment group, a history of fluctuating or rapidly deteriorating hepatic function or the production of widely varying or worsening clinical and/or laboratory signs of hepatic impairment within the screening period
25. If destined for the healthy control group, a history of prescription or over-the-counter (OTC) drug use within 7 days or 5 half-lives of the drug, whichever is longer, prior to D0
26. If destined for the healthy control group, a history of liver disease or liver injury as indicated by an alanine aminotransferase (ALT), aspartate aminotransferase (AST), > 2.5 × the upper limit of normal (ULN) at screening, or serum bilirubin > 1.5 × ULN
27. If destined for the healthy control group, evidence of HBV or HCV infection.
28. Any other serious medical condition that, in the opinion of the investigator, would pose a significant risk to the subject or interfere with the interpretation of safety, PK, or PD data.

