AUC_{0-24} , AUC_{0-t} , and $AUC_{0-\infty}$ will be calculated using the linear trapezoidal linear interpolation method, using actual elapsed time values. If the actual collection time is unknown the nominal collection time may be used for the purposes of PK parameter estimation. For the purpose of calculating AUC, all missing values will be treated as missing in the PK analysis and excluded from analysis except when they occur at pre-dose where they will be set to zero. All values that were below the limit of quantitation (BLOQ) prior to T_{max} will be set to zero. BLOQ values that occur after T_{max} will be set to missing. When ≥ 2 consecutive plasma concentrations that are BLOQ are encountered after T_{max} , these and all subsequent values will be excluded from the analysis.

$AUC_{0-\infty}$ will be calculated as outlined below:

$AUC_{0-\infty} = AUC_{last} + (C_{last} / \lambda_z)$, where C_{last} is the last temporal quantifiable plasma concentration corresponding to T_{last} .

The proportion of $AUC_{0-\infty}$ due to extrapolation (AUC_{extr}) will be calculated and expressed as a percentage. $AUC_{0-\infty}$ values will be considered unreliable estimates if the AUC_{extr} is greater than 20% and will be excluded from summary tables but will be listed.

CL/F will be calculated as $Dose/AUC_{0-\infty}$.

V_z/F will be calculated as $Dose/(\lambda_z \times AUC_{0-\infty})$.

$T_{1/2}$ will be calculated as $0.693/\lambda_z$.

The fraction unbound (f_u) will be calculated as free drug concentration/total drug concentration.

The apparent clearance relative to the unbound drug concentration (Cl_u/F) will be calculated as $Cl_u/F = Dose/AUC_u$.

Listings of plasma concentrations by Subject Number, hepatic function group, and timepoint will also be provided.

To assess the effect of moderate hepatic impairment on the PK of bexagliflozin, an analyses of variance (ANOVA) with a fixed effect corresponding to the hepatic function group (normal or moderate hepatic impairment) will be fitted to the natural logarithmic transformation of PK parameters (C_{max} , AUC_{0-t} and $AUC_{0-\infty}$). The 90% confidence intervals will be constructed for the ratio of least squares (LS) geometric means of PK parameters (total and unbound C_{max} , AUC_{0-t} and $AUC_{0-\infty}$) for the moderate hepatic function group vs the normal group, with 80-125% defined as the boundaries for subjects in the PK Population.

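### Controls are defined as having normal hepatic function, but the only numeric liver rule for them admits abnormal ALT, AST and bilirubin and sets no albumin or INR limit

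*Protocol*

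**What the plan says.** **The definition.** Protocol 4.1 plans "eight control subjects (healthy subjects with normal hepatic function", and Protocol 5.4 repeats the requirement for evaluable controls. Protocol 3.2.1 describes the comparison as being with "demographically matched subjects with normal hepatic function". SAP 7.2 carries the definition into the model, whose single fixed effect is the "hepatic function group (normal or moderate hepatic impairment" factor, and SAP 7.3 uses the same two groups for the pharmacodynamic summaries.

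**The numeric rule.** Criterion 26 of Protocol 4.3 excludes a prospective control for liver disease or injury as shown by ALT or AST "> 2.5 × the upper limit of normal (ULN) at screening, or serum bilirubin > 1.5 × ULN". Values at or below those multiples pass. No criterion gives an albumin or INR limit for controls, and controls do not have to be scored on the Child-Pugh scale.

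**The qualitative safeguards.**
- Inclusion criterion 7 asks controls to "Be in general good health with matching demographics and baseline characteristics".
- Criterion 18 excludes, for all subjects, "hepatocellular carcinoma, acute liver disease, severe hepatic encephalopathy, or biliary liver cirrhosis".
- Criterion 19 excludes active alcoholic hepatitis.
- Criterion 25 excludes recent prescription or over-the-counter drug use in controls.
- Criterion 27 reads "If destined for the healthy control group, evidence of HBV or HCV infection".
- Criterion 28 lets the investigator exclude serious conditions that would "interfere with the interpretation of safety, PK, or PD data".

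**The concern.** Every exposure ratio in this trial has the same eight controls as its denominator. A stated entry rule admits people whose liver tests contradict the stated definition of that denominator, and nothing in either document says how normal function is to be verified. Chronic non-viral liver disease is not named among the exclusions. Criterion 26 does mention a history of liver disease, but its wording ties that history to the laboratory multiples.

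The likely direction of any bias is clear, subject to one condition. If hepatic dysfunction raises exposure, which is the possibility under study, a mildly affected control raises the reference geometric mean and moves the ratio towards 1. That would make the effect of moderate impairment look smaller than it is. A confidence interval does not account for a bias of this kind.

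**Working it through.** The plan has no figure to reproduce: Protocol 9.2 and SAP 3.5 state that the sample size has no formal statistical basis, and neither gives a between-subject CV. The check is therefore a comparison of texts, followed by an illustration.

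**1. Definition against rule**

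| Liver measure | Numeric limit for controls | Measured at screening? |
|---|---|---|
| ALT, AST | excluded only above 2.5 × ULN | yes |
| Total bilirubin | excluded only above 1.5 × ULN | yes |
| Albumin | none | yes |
| INR | none | yes |

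The measurements come from Protocol Table 1, Protocol 7.1 and Appendix 1. A control with, say, ALT at 2 × ULN meets the numeric rule but does not have a normal liver panel. The two statements cannot both define the group.

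**2. Illustration of dilution**

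Assume that *k* of the 8 controls have exposure raised by a proportion *m*. On the log scale the control mean rises by (*k*/8) × ln(1 + *m*), so the observed ratio is the true ratio multiplied by (1 + *m*)^(−*k*/8). Both *k* and *m* are assumptions. With *k* = 2 the exponent is −0.25:

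- *m* = 10%: 1.10^(−0.25) = 0.976, a fall of 2.4%
- *m* = 20%: 1.20^(−0.25) = 0.955, a fall of 4.5%
- *m* = 30%: 1.30^(−0.25) = 0.937, a fall of 6.3%

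A true ratio of 1.50 would be seen as 1.46, 1.43 or 1.40 respectively.

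**3. Comparison with the precision of the trial**

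For 8 against 8 with a single group factor, the 90% interval is the ratio multiplied and divided by exp[t(0.95; 14) × √ln(1 + CV²) × √(2/8)], where t(0.95; 14) = 1.761 and √(2/8) = 0.5. The CV is assumed.

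| Assumed CV | √ln(1 + CV²) | Interval factor |
|---|---|---|
| 20% | 0.198 | 1.19 |
| 30% | 0.294 | 1.30 |
| 40% | 0.385 | 1.40 |
| 50% | 0.472 | 1.52 |

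Even at a CV of 20% the lower limit lies 1 − 1/1.19 = 16% below the estimate. A shift of 2% to 6% is well inside that.

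**The case against.** The best reply is that entry is narrower than the numbers suggest. The enrolment text itself asks for normal hepatic function. The good-health, viral hepatitis, acute liver disease, alcohol and drug-use criteria would turn away most people with abnormal liver tests, and the investigator has further discretion. Abnormal controls would also be visible: SAP 6.1 and 8.3 summarise baseline laboratory values by group, SAP 6.3.4 and 8.4.2 list and flag out-of-range results, and SAP 1 permits justified changes to the analysis. No hypothesis is formally tested (SAP 3.3).

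This lowers the likelihood and the probable size of the problem, and that much stands. It does not remove the contradiction. None of these criteria says what normal means, and a site that applies criterion 26 as written may enrol a control with abnormal tests in good faith. Listings would show it afterwards, but no analysis is planned to address it.

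A reader might infer three stronger things, which the documents do not support:

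- **That controls may have any albumin or INR.** There is no numeric limit, but the qualitative criteria do restrict entry. The drug-use exclusion, for example, makes a drug-induced rise in INR unlikely.
- **That an eligible control could be shown to be impaired because the Child-Pugh total falls in class A, labelled mild.** Five items at one point each give a minimum total of 5, so a person with entirely normal findings is also in class A. ALT and AST are not Child-Pugh items. Bilirubin at 1.5 × ULN stays below 2 mg/dL for an assumed ULN of 1.0 to 1.3 mg/dL (1.5 to 1.95), and so scores one point.
- **That low albumin in controls must shrink the unbound contrast.** The documents give no relation between albumin and unbound fraction for this drug. Under SAP 7.2 the fraction is measured in each subject and applied to that subject's own concentrations. A higher fraction could also lower total exposure, which would move the total ratio the other way.

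**Conclusion.** The point holds as an inconsistency between the definition of the reference group and the rule that admits people to it. The bias would be towards a ratio of 1, provided that mild hepatic dysfunction raises exposure.

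Its size cannot be estimated from the documents. They do not link modestly raised ALT, AST or bilirubin to bexagliflozin exposure; Protocol 1 says that the contributions of different organs to its metabolism are unknown; and they do not indicate how many controls might be affected. The 2% to 6% figure is an illustration that rests on 2 affected controls and a 10% to 30% rise. A larger understatement needs more affected controls or a larger rise, and nothing in the documents supports either. This is a cheap improvement to the design. It does not show that the trial would miss an effect.

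**What to change.** Reconcile criterion 26 with the definition in Protocol 3.2.1, 4.1 and 5.4. One wording would require controls' screening ALT, AST, total bilirubin, albumin and INR to be within the laboratory's normal range, or within a stated tight limit and not judged clinically significant. The sponsor should choose and state the limit.

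The cost is a short amendment and no new tests. There would be some extra screen failures, and these matter somewhat because each control is individually matched on age, weight, sex and smoking status.

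If enrolment is complete, report the controls' baseline values for these five tests. Before database lock, add to the SAP a sensitivity estimate of the ratios that omits controls with abnormal values. The loss of precision is modest. With 6 controls against 8 patients the standard-error multiplier rises from 0.500 to √(1/8 + 1/6) = 0.540, and t(0.95; 12) = 1.782. At an assumed CV of 30% the interval factor becomes exp(1.782 × 0.294 × 0.540) = 1.33, compared with 1.30 for all 16 subjects.
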